	Participant (J)	4.70E+13 vg	1.71E+14 vg	2.18E+14 vg
Cohort 1	Participant (I)	4.70E+13 vg	1.71E+14 vg	2.18E+14 vg
(Mid-Dose)	Participant (I)	4.70E+13 vg	1.71E+14 vg	2.18E+14 vg
	Participant (I)	8.15E+13 vg	2.74E+14 vg	3.56E+14 vg
Cohort 2 (High-Dose)	Participant (I)	8.15E+13 vg	2.74E+14 vg	3.56E+14 vg

Note: Dosing based on final titer of 3.26E+13 vg/mL (1:1 mixture of AAVrh8-HEXA:AAVrh8-HEXB)

Stage 2 dosing regimen will be determined based on Stage 1 results.

Duration of treatment: AXO-AAV-GM2 will be administered as a single, two-part procedure

Reference Therapy, Dosage and Mode of Administration: N/A

Criteria for Evaluation:

Stage 1

Stage 1 Primary Endpoint:

• The incidence, severity, seriousness, and relatedness to treatment of treatment emergent adverse events (TEAEs) as graded NCI CTCAE v5.0

Stage 1 Secondary Endpoints:

- Safety and immunologic response endpoints
- Changes in vital signs including weight
- Changes in physical examination findings
- Changes in clinical safety laboratory tests
- Immunosuppression response markers

Stage 1 Exploratory Endpoints:

- Changes from baseline in developmental age-appropriate clinical function assessments
 - Infantile participants: Bayley Scales of Infant and Toddler Development, Third
 Edition (BSID-III), Hammersmith Infant Neurological Examination Section 2
 (HINE-2; motor), Clinical Global Impression (CGI), Vineland-3 Neurological exam

Confidential Page 13 of 97

Version 8.0, 09 June 2023

- Juvenile participants: Neurocognitive function (as measured by the Wechsler, WPSSI, BSID-III depending on the participant's developmental age), Vineland-3, CGI, Neurological exam, fine and gross motor function and classification (as measured by GMFM-88, GMFC-MLD, timed motor function tests, 9-hole peg test, and the Manual Ability Classification System (MACS))
- Biomarker changes from baseline in:
 - Serum HEXA activity level
 - CSF HEXA activity level
 - GM2 ganglioside in CSF
- Change from baseline in brainstem auditory evoked response (BAER) and visual evoked response (VER) from baseline to Week 12 and Week 48
- MRI brain volume and Diffusion Tensor Imaging (DTI) indices of myelination and brain water change from baseline to Week 12 and Week 48
- MRS indices of metabolite accumulation change from baseline to Week 12 and Week 48

Stage 1 Juvenile-Onset Participant Efficacy:

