Biologic and clinical efficacy endpoint measures will be performed for juvenile-onset participants enrolled in Stage 1 of the study. These endpoints will be analyzed in a descriptive manner, separately from that of the infantile-onset participants.

Stage 2

Stage 2 Primary Endpoint(s):

- Clinical Function: BSID-III Gross Motor domain change from baseline to Week 48 (12 months)
- Surrogate Biologic Marker: CSF HexA activity change from baseline to Visit 9/Week 48

Stage 2 Secondary Endpoints(s):

- Changes in Biomarkers:
 - Serum HexA activity levels change from baseline to Week 48 (12 months)
 - CSF GM2 ganglioside levels change from baseline to Week 48 (12 months)
- Biodistribution: Serum and CSF vector DNA levels will be measured over 48 weeks (12 months) to assess the pharmacokinetics of AXO-AAV-GM2
- Clinical Function:
 - BSID-III Composite score change from baseline over Week 48
 - Proportion of Motor Milestone responders based on Hammersmith Infant Neurological Examination (HINE) Section 2 from baseline to Week 48

Responder defined as:

i. The participant demonstrated at least a 2-point increase in the motor milestones category of ability to kick or achievement of maximal score on that category

Confidential Page 14 of 97

Clinical Study Protocol: AXO-GM2-001

Version 8.0, 09 June 2023

(touching toes), or a 1-point increase in the motor milestones of head control, rolling, sitting, crawling, standing, or walking

AND

- ii. Among the 7 motor milestone categories (with the exclusion of voluntary grasp), the participant demonstrated improvement (as defined in [i]) in more categories than worsening
- Proportion of infantile-onset participants maintaining the ability to sit without support as assessed in HINE Section 2 at Week 48

Stage 2 Exploratory Endpoint(s):

- Changes from baseline in developmental age-appropriate clinical function assessments as measured by BSID-III, HINE-2 (Motor), CGI, Neurologic exam, and Vineland-3
- Biomarker changes from baseline over 5 years in:
 - Serum HEXA activity level
 - CSF HEXA activity level
 - GM2 ganglioside in CSF
- Change from baseline in brainstem auditory evoked response (BAER) and visual evoked responses (VER) from baseline to Week 12, Week 24, and Week 48
- MRI brain volume and Diffusion Tensor Imaging (DTI) indices of myelination and brain water change from baseline to Week 12 and Week 48
- MRS indices of metabolite accumulation change from baseline to Week 12 and Week 48

Long-term Follow-up

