- 25. Participants must have a swallow evaluation test performed within 6 months prior to AXO-AAV-GM2 administration to assess the risk of aspiration. If aspiration risk is identified, it must be clinically managed prior to surgical procedures. Participants must have a swallow evaluation test performed at baseline and a clinical assessment of swallowing and a swallow study, if warranted, at Visit 9 (Week 12), Visit 12 (Week 24), Visit 13 (Week 48), Visit 15 (Week 96) and yearly thereafter for Years 3-5 (see Table 16).
- 26. BAER/VER/SSEP should be conducted without sedation or a prolongation of, or another episode of general anesthesia.
- 27. May be completed if visit occurs in person however not if the visit is completed as a tele-health
- 28. Tele-health will occur if Pt does not come to site in person

AN - As Needed

Confidential Page 57 of 97

Clinical Study Protocol: AXO-GM2-001

Version 8.0, 09 June 2023

Confidential Page 58 of 97

Clinical Study Protocol: AXO-GM2-001

Version 8.0, 09 June 2023

 Table 15:
 Schedule of Infantile-Onset Participant Assessments

Schedule of Activities	Visit A	Visit B	Visit C	Visit D	Visit 1a	Visit 1b	Visit 2	Visit 3	Visit 4	Visit 5	Visit 6	Visit 7	Visit 8	Visit 9	Visit 10	Visit 11	Visit 12	Visit 13
	Week - 8	Day -16	Day -7	Day -2	Day	Day	Day	Day	Day	Week	Week	Week	Week	Week	Week	Week	Week	Week
	±28d	±5d	±3d	-2 ±1d	-	2	8 ±1d	15 ±3d	22 ±3d	4 ±3d	6 ±4d	8 ±5d	10 ±4d	12 ±7d	16 ±7d	20 ±7d	24 ±7d	48 ±7d
ICF	X*	Х																
Inclusion/Exclusion Criteria	X*	Х																
Genetic Confirmation ¹	X*																	
Vital Signs 11	X*	Х	X	X	Х	X	X	X	X	X	X	X	X	X			X	X ²³
Weight	X*	X	X	X			X	X	X	X	X	X	X	X			X	X ²³
Height	X*	X	X											X			X	X ²³
Physical Examination	X*	X		X	X	X	X	X	X	X	X	X	X	X			X	X ²³
Neurologic Examination ¹²	X*			X		X	X	X	X	X	X	X	X	X			X	X ²³
Tele-health follow-up															X	X		X ²⁴
Tele-health Neuro Exam																		X ²⁴
Ophthalmology Exam			X															
HINE-2	X*									X				X			X	X ²³
BSID-III	X*									X				X			X	X ²³
Clinical Global Impression	X*									X				X			X	X
CBC with auto-differential ⁶	X				X	X	X	X	X	X	X	X	X	X			X	X ²³
Comprehensive metabolic panel ⁶	Х				Х	Х	X	Х	X	X	Х	Х	X	Х			X	X ²³
hsCRP	X				X	X	X	X	X	X	X	X	X	X			X	X ²³
GGT – AN due to elevated liver enzymes	AN				AN	AN	AN	AN	AN	AN	AN	AN	AN	AN			AN	AN
PT, PTT, INR, Blood Typing ⁶				X														
Total hemolytic complement (CH50) – AN due to platelet count decrease ⁶	AN				AN	AN	AN	AN	AN	AN	AN	AN	AN	AN			AN	AN

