12. ASSESSMENT OF EFFICACY

Assessment of efficacy within this study will include:

- CSF HexA activity and GM2 ganglioside level
- Serum HexA activity
- BSID-III
- HINE-2
- MRI
- DTI
- MRS
- BAER
- VER
- Clinical Global Impression
- Vineland-3
- Wechsler scale (Wechsler 5, WPPSI, etc)
- GMFM-88
- GMFC-MLD
- 9-Hole Peg Test
- The Pediatric Balance Scale
- Timed Motor Function Tests (10 Meter Walk/Run, Time to Rise from Floor, Time Up 4 Stairs)
- SSEP

Please see the Study Schedule of Events (Table 14 and Table 15) for the timing of these assessments.

Several assessments included in this study will be administered by raters trained in the administration of the assessment. To minimize variability, it is preferred that the same rater administer the same scale to the same participant throughout the study wherever possible, at the same time during the clinic visit.

Confidential Page 76 of 97

UMass Chan Medical School Clinical Study Protocol: AXO-GM2-001 Version 8.0, 09 June 2023

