13.8. Brainstem Auditory Evoked Response (BAER)

Standard BAER testing for auditory acuity will be documented.

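### Table 15 schedules neither BAER/VER nor Vineland-3, so the infantile change-from-baseline exploratory endpoints built on them cannot be formed as planned

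*Combined protocol and SAP*

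**What the plan says.** **BAER/VER.** The Stage 1 exploratory endpoint is the change in BAER and "visual evoked response (VER) from baseline to Week 12 and Week 48". In the same list the clinical-function endpoint is split into infantile and juvenile instruments; the BAER/VER endpoint is not, so it covers both groups. The Stage 2 exploratory endpoint is "Change from baseline in brainstem auditory evoked response (BAER) and visual evoked responses (VER) from baseline to Week 12, Week 24, and Week 48", and Stage 2 enrols infantile-onset participants only.

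**Vineland-3.** For Stage 1 infants, the change-from-baseline clinical-function measures include "Clinical Global Impression (CGI), Vineland-3 Neurological exam". For Stage 2 they are given "as measured by BSID-III, HINE-2 (Motor), CGI, Neurologic exam, and Vineland-3".

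**Schedule.** Section 12 lists BAER, VER and Vineland-3 among the efficacy assessments and adds: "Please see the Study Schedule of Events (Table 14 and Table 15) for the timing of these assessments". Sections 8.1.1 and 8.1.2 put infantile participants of both stages on Table 15, the "Schedule of Infantile-Onset Participant Assessments", until Week 48. After that they move to Table 17 (Section 8.1.3). Juveniles follow Table 14, which does have a BAER/VER/SSEP row, with the condition in footnote 26 that "BAER/VER/SSEP should be conducted without sedation or a prolongation of, or another episode of general anesthesia".

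**The concern.** A change from baseline needs a value before gene transfer and a value at each named visit. If the infantile schedule asks for neither, a site that follows the protocol exactly will not produce the endpoint. Gene transfer is a single procedure, so the pre-dose value is lost for good in each child dosed under the table.

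The study is uncontrolled, so a child's own baseline is the natural reference for these measures. Sections 7.1.3 and 7.2.3 also set peripheral and central nervous system integrity as an exploratory objective in each stage, and BAER/VER is the listed endpoint that serves it most directly.

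**Working it through.** The plan gives no figure to reproduce. The check compares the visits that each endpoint needs with the visits at which the tables schedule the assessment.

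| Measure (infantile participants) | Time points needed | Scheduled in Table 15 | First scheduled in Table 17 |
|---|---|---|---|
| BAER/VER, Stage 1 | baseline, Weeks 12, 48 (3) | 0 of 3 | Week 144, once only |
| BAER/VER, Stage 2 | baseline, Weeks 12, 24, 48 (4) | 0 of 4 | Week 144, once only |
| Vineland-3, both stages | baseline and at least one later visit (none named) | none | Week 72 |

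1. **Table 15, all rows and footnotes 1 to 24.** None mentions BAER, VER, SSEP or Vineland. The other four instruments in the infantile clinical-function endpoint (BSID-III, HINE-2, CGI, neurologic examination) are all scheduled at Visit A. So 4 of 5 have a baseline and Vineland-3 does not.

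2. **Table 17.** BAER/VER/SSEP appears at Week 144 alone, which is not a time point of either endpoint. Vineland 3 appears at Weeks 72, 96, 120, 144, 168, 192 and 240. That is seven post-treatment values with no pre-treatment value to subtract.

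3. **Table 14, for contrast.** BAER/VER/SSEP is scheduled at Visit A and Weeks 12, 24 and 48. The Stage 1 endpoint can therefore be computed for juveniles (3 of 3 time points). The gap is confined to infants.

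4. **Could rows have been lost in reading the PDF?** Each of the 24 Table 15 footnotes belongs to a visible row or cell, and none concerns these tests. Table 14 kept both its BAER row and its footnote 26. Loss of rows is unlikely.

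5. **Other text that might supply a visit.** Section 13.8 says "Standard BAER testing for auditory acuity will be documented" and names no visit. Table 14 footnote 22 expects all participants to have the Vineland 3, but it is attached to the neuro-cognitive row of the juvenile table, and Table 15 has no such row.

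6. **Children concerned.** Table 13 lists infantile slots of 1 (Low) + 2 (Mid) + 2 (High) = 5, plus one open to either type, so 5 or 6. With a full Stage 2 of 10 that makes 10 + 5 = 15 or 10 + 6 = 16. Table 13 shows nine of the twelve planned Stage 1 participants and extra participants are allowed, so this is a count of listed slots and not a fixed total.

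**The case against.** The strongest reply is that Stage 2 is provisional. The Synopsis says its design and endpoints will be refined from Stage 1 data, Section 8.1.2 allows the number enrolled to change, and Section 13.4.7 shows that the sponsor intends to add assessments to the schedule by amendment. This stands in part: the Stage 2 gap could still be closed before anyone is dosed in that stage. It does not help Stage 1 infants, who follow the same table. Section 13.4.7 defers viral shedding explicitly, and nothing comparable is said of BAER/VER or Vineland-3.

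A second reply is that Section 12 is a pooled list. It includes tools named as endpoint measures only for juveniles, so its pointer to both tables does not promise a Table 15 row for every entry. That is fair. The contradiction rests on the endpoint lists set against Table 15, and Section 12 only adds that no other source of timing is named.

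A third reply is that little depends on these measures. They are exploratory, Stage 1 is analysed descriptively, and no formal hypothesis is tested. This stands and limits the weight of the point.

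A reader might infer more than the documents support:

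- **That infants have no usable data on either measure.** Table 17 schedules seven Vineland 3 assessments, which give a within-child course from Week 72, and one BAER/VER assessment. What is lost is change from baseline.
- **That dosed infants certainly have no baseline.** The schedule does not ask for one, but it cannot show whether a site collected one anyway.
- **That the fault reaches the primary or secondary endpoints.** It does not. Sampling for vector DNA, a Stage 2 secondary endpoint, is a separate clarification and not part of this point.

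**Conclusion.** Wrong as written: the endpoint lists and the infantile schedule contradict each other. For infants, Table 15 provides 0 of 3 BAER/VER time points in Stage 1 and 0 of 4 in Stage 2, and Vineland-3 has no baseline in either stage. Followed as it stands, the plan cannot yield these change-from-baseline results.

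The consequence is modest but cannot be reversed for a child already dosed. Only exploratory endpoints are involved, and the juvenile BAER/VER endpoint is intact. The conclusion assumes that Table 15 as read is complete and that infants are assessed by schedule. The Stage 2 part also assumes that its schedule is not amended first.

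**What to change.** Before further infantile participants are dosed:

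1. **Vineland-3.** Add it to Table 15 at Visit A and at least Week 48, both visits where BSID-III is already done. The endpoint names no time points, so the other BSID-III visits (Weeks 4, 12 and 24) are optional. Alternatively, remove Vineland-3 from the infantile change-from-baseline endpoints.
2. **BAER/VER.** Either add it to Table 15 at the visits the endpoints name, under the condition in Table 14 footnote 26, or limit the endpoint to juveniles in Stage 1 and remove it from Stage 2.
3. **Infants already dosed without a baseline.** Report observed values, not change from baseline, and say so in the analysis plan.

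If Vineland-3 is kept, the cost is that assessment at visits already taking place. For BAER/VER it is either added testing in infants or the loss of one exploratory endpoint for them.

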3. LIST OF ABBREVIATIONS AND DEFINITIONS OF TERMS

The following abbreviations and specialist terms are used in this study protocol.

Table 4: Abbreviations and Specialist Terms

Abbreviation or Specialist Term	Explanation
AAV	Adeno-associated virus
AE	Adverse Event
AESI	Adverse event of special interest
ADR	Adverse drug reactions
ALT	Alanine aminotransferase
AST	Aspartate aminotransferase
BAER	Brainstem auditory evoked response
BiTh	Bilateral thalamic
BSA	Body surface area
BSID-III	Bayley Scales of Infant and Toddler Development, 3rd Ed
BUN	Blood urea nitrogen
CBA	Chicken β-actin
CBC	Complete blood count
CED	Convection enhanced delivery
CMP	Clinical Monitoring Plan
CNS	Central nervous system
CRF	Case report form
CRA	Clinical research associate
CRO	Contract research organization
CRIM	Cross reactive immunological material
CSF	Cerebrospinal fluid
CT	Computed Tomography
CTL	Cytotoxic T lymphocytes
DTI	Diffusion tensor imaging
DSMC	Data Safety Monitoring Committee
ECG	Electrocardiogram
EDC	Electronic Data Capture
EEG	Electroencephalogram
ELISA	Enzyme-linked immunosorbent assay
ERT	Enzyme replacement therapy
FDA	Food and Drug Administration
FBS	Fetal bovine serum

Confidential Page 22 of 97

UMass Chan Medical School Clinical Study Protocol: AXO-GM2-001 Version 8.0, 09 June 2023

Abbreviation or Specialist Term	Explanation
GAA	Acid α-glucosidase
GCP	Good Clinical Practice
GMO	Genetically modified organism
GM2	Disialotetrahexosylganglioside
Hex	Hexosaminidase enzyme
HexA	Hexosaminidase A enzyme
HEXA	HEXA gene
HEXB	HEXB gene
HIPAA	Health Insurance Portability and Accountability Act
HINE	Hammersmith Infant Neurological Examination
HIV	Human immunodeficiency virus
Hs-CRP	High-sensitivity C-Reactive Protein
ICH	International Conference on Harmonization
ICM	Intracisternal Magna
ICP	Intracranial Pressure
ICV	Intracerebroventricular
IEC	Independent Ethics Committee
IL	Interleukin
IND	Investigational new drug
IPa	Intraparenchymal
IRB	Institutional Review Board
IRR	Infusion related reaction
ITT	Intent to treat
IT	Intrathecal
ITI	Immune tolerance induction
IV	Intravenous
IVIG	Intravenous immunoglobulin
LFTs	Liver function tests
LP	Lumbar puncture
LDH	Lactate dehydrogenase
LSD	Lysosomal storage disorder
LTFU	Long term follow-up
MedDRA	Medical Dictionary for Regulatory Activities
MMRM	Mixed-effect model repeated measure
MRI	Magnetic resonance imaging
MRS	Magnetic resonance spectroscopy

Confidential Page 23 of 97

UMass Chan Medical School Clinical Study Protocol: AXO-GM2-001 Version 8.0, 09 June 2023

Abbreviation or Specialist Term	Explanation
NCI	National Cancer Institute
NHP	Non-human primate
NHS	Natural history study
NIH	National Institute of Health
PBMCs	Peripheral blood mononuclear cells
PBS	Phosphate buffered saline
PICU	Pediatric Intensive Care Unit
PI	Principal Investigator
PML	Progressive multifocal leukoencephalopathy
PO	Per os
PT	Prothrombin time
PTT	Partial thromboplastin time
RBC	Red blood cell
SADE	Serious adverse device effect
SAE	Serious adverse event
SD	Sandhoff disease
SMA	Spinal muscular dystrophy
SOP	Standard operating procedure
TEAE	Treatment emergent adverse event
Th	thalamus
TSD	Tay-Sachs disease
UNL	Upper normal limit
Vd	Volume of distribution
VER	Visual evoked responses
Vi	Volume of infusion
WBC	White blood cell
YO	Year old

Confidential Page 24 of 97 UMass Chan Medical School AXO-AAV-GM2

Clinical Study Protocol: AXO-GM2-001

Version 8.0, 09 June 2023

4. INTRODUCTION

Tay-Sachs disease (TSD) and Sandhoff disease (SD) are lysosomal storage disorders (LSDs) caused by a deficiency in the enzyme β -N-acetyl-D-hexosaminidase A (HexA), which is responsible for GM2 ganglioside degradation. (Ferreira and Gahl 2017) Gangliosides are the main glycolipids of neuronal cell plasma membranes which ensure normal cellular activities. (Sandhoff and Harzer 2013) HexA is an isoenzyme consisting of α and β subunits which are encoded by the *HEXA* and *HEXB* genes, respectively. TSD is caused by mutations in *HEXA* encoding the α subunit, whereas SD is caused by mutations in *HEXB* encoding the β subunit. Both forms of GM2 gangliosidosis are caused by overwhelming storage of GM2 ganglioside within neurons throughout the central nervous system (CNS), which is normally degraded in the lysosome by the isozyme HexA. The resulting neuronal dysfunction and cell death induces the primary symptoms of the disease: motor impairment, seizures, and sensory impairments. The progression and symptoms associated with TSD and SD are virtually indistinguishable as they arise from dysfunction of the same lysosomal enzyme (HexA) and storage product (GM2).

There are 3 categories of GM2 gangliosidoses defined by the age of symptom onset: infantile, juvenile, and late-onset. Those with infantile-onset have the most severe mutations and despite achieving very early developmental milestones at expected age, quickly plateau and regress. Infantile-onset individuals are often diagnosed due to developmental delays, hypotonia, and exaggerated startle response beginning on average at approximately 5 months of age; however, diagnosis is made on-average at approximately 13 months of age (Smith et al. 2012). These infants and toddlers eventually develop hypotonia, seizures, swallowing difficulties and progress to a semi-vegetative state. Bley and colleagues reported the first survival analysis of patients affected by infantile-onset GM2 gangliosidosis, with only half surviving beyond the age of 3 years and one-quarter surviving to the age of 5 years (Bley et al. 2011). Juvenile-onset GM2 symptomatology generally develops at approximately 5 years of age (range of 1.5 - 15 years) with speech, gait or learning difficulties (Maegawa et al. 2006). Death occurs in a similar fashion to infantile-onset, but typically occurs in the second decade of life due to the slower rate of disease progression. Late-onset GM2 patients often have a normal lifespan, but develop gait abnormalities (often wheelchair bound), swallowing and speech difficulties, peripheral neuropathy as well as psychiatric manifestations.

The rate of storage, clinical disease onset and progression severity is largely determined by the particular mutation and associated level of residual HexA activity (Solovyeva et al. 2018). Conzelmann et al. reported a correlation between residual activity of HexA and the severity of GM2 gangliosidosis, through an assay system using radiolabeled GM2 ganglioside as a substrate in human fibroblast extracts. (Conzelmann et al. 1983) Hex A activities for infantile, juvenile, and adult-onset patients were ≤0.1, 0.5, and 2-4% of normal, respectively. Importantly, healthy probands were found to possess activities of 11% to 20% of normal, suggesting that low levels of residual HexA activity may be sufficient to achieve ganglioside normalization. This concept is further elucidated in Figure 2 below, adapted from Leinekugel, et al 1992 (Leinekugel et al. 1992).

[figure not shown]
Confidential Page 25 of 97

UMass Chan Medical School AXO-AAV-GM2

Clinical Study Protocol: AXO-GM2-001

Version 8.0, 09 June 2023

Figure 2: Residual Activity of HexA and GM2 Turnover in Skin Fibroblast Cell Culture

Adapted from Leinekugel et al. 1992

This study demonstrated a correlation between HexA activity and clinical disease severity. Groups corresponding to infantile, juvenile, and adult-onset disease forms could be distinguished with limited overlap in residual enzyme activity and were well separated from heterozygotes. Small increases in HexA activity were associated with milder phenotypes from the severe infantile-onset form to the mild adult-onset form. This suggests a range of approximately 5-15% of normal HexA activity may result in adequate ganglioside clearance and potentially an improved disease course with stabilized motor/neurologic function and achievement of developmental milestones.

HexA expression in serum and cerebrospinal fluid (CSF) will be assessed in this study and holds the potential to serve as a surrogate marker of disease. Given the known pathophysiology and direct-to-CNS route of administration, CSF HexA expression should be the most likely biologic surrogate endpoint that would predict clinical benefit.

There are no FDA-approved treatments for GM2 gangliosidoses and there is no effective clinical treatment generally. Although Miglustat, a glucosylceramide synthase inhibitor approved for monotherapy in adult patients with mild to moderate type 1 Gaucher disease, is known to cross the blood-brain barrier and commonly used off-label in TSD and SD patients, it is associated with peripheral neuropathy, tremor, diarrhea and weight loss (ZAVESCA® Package Insert 2011) and has not been observed to result in marked improvement in symptom management or disease progression. (Regier et al. 2016, Bembi et al. 2006, Maegawa et al. 2009, Shapiro et al. 2009) Current medical care can increase lifespan of affected patients through gastric tube feeding, seizure management, and vigilant pulmonary supportive care, but the quality of life is very poor, and patients eventually succumb to respiratory infection secondary to aspiration pneumonia (the most common cause of death in infantile gangliosidoses). There is a significant unmet clinical need for effective treatments for TSD and SD patients.

[figure not shown]
Confidential Page 26 of 97

[figure not shown]
